3.2.2 Study Period and Evaluation Period

Study period: The study period is defined as the period from the time of obtaining the informed consent to the time of completion of the end-of-study assessment or discontinuation assessment (for subjects who entered the follow-up period, to the time of completion or termination of the follow-up).

Screening: Subjects providing informed consent were screened for eligibility to select subjects meeting all of the inclusion criteria and none of the exclusion criteria (36 subjects with a few reserve subjects).

Evaluation period: The evaluation period is defined as the period from completion of dosing of the investigational product in Period I to completion of the end-of-study assessment or discontinuation assessment.

End-of-study assessment: The prespecified observations and tests were performed as the end-of-study assessment, 7 days (± 2 days) after the last dose of the investigational product.

3.3 Schedule of Study Procedures

- a) At the time of withdrawal, perform the same tests as would be performed in the end-of-study assessment.
- b) Collecting serious adverse events was started after informed consent was obtained. Collecting the other adverse events was started after the first administration of the investigational product.

3.4 Sample Size and Power Considerations

Total of 36 subjects

[Rationales for setting]

A sample size of 36 subjects was set to ensure 30 completing subjects allowing for 6 dropouts based on the results of a bioavailability study of TIGLUTIC® (Riluzole suspension) administered orally versus NGT administration (Benjamin Rix Brooks et al., 2019) and practical experiences in preceding studies.

4 PLANNED ANALYSIS

4.1 Final Analysis

This SAP will be finalized before database lock. Final data analysis will be performed after database lock.

5 ANALYSIS POPULATIONS

Pharmacokinetic (PK) analysis will be performed on the PK analysis set (PKPOP). Safety analysis will be performed on the safety analysis set (SAF). The definitions of the analysis sets are provided below. The detailed handling of subjects will be determined by the sponsor, by the time of database lock.

(1) PK analysis set (PKPOP)

The PK analysis set will consist of all subjects who received at least 1 dose of the investigational product and have evaluable PK data.

(2) Safety analysis set (SAF)

The SAF will consist of all subjects who received at least 1 dose of the investigational product.

6 STATISTICAL CONSIDERATIONS

6.1 Descriptive Statistics

(1) Non-PK related

Continuous data will be summarized descriptively using the number in the analysis set (N), the number of observations (n), mean, SD, median, minimum and maximum. Categorical data will be summarized using frequency counts and percentages. The denominator for the percentages will be the total number of subjects in the treatment/group and analysis population applied, unless otherwise specified.

(2) PK related

1) Plasma concentrations

Plasma concentrations will be summarized descriptively using N, n, mean, SD, CV%, median, minimum and maximum.

2) Pharmacokinetic parameters

The plasma PK parameters will be summarized descriptively using N, n, mean (i.e. arithmetic mean), SD, CV%, median, minimum, maximum, geometric mean and geometric CV%.

CV% and Geometric CV% will be calculated as follows:

$$CV\% = \frac{SD}{\text{arithmetic mean}} \times 100$$

$$\text{Geometric CV\%} = \sqrt{[\exp(\sigma^2) - 1]} \times 100$$

where σ represents the SD calculated from the natural logarithmic transformed value of parameters.

6.2 Statistical Tests and Estimates

No statistical tests will be performed. Confidence level will be 0.90, so that two-sided 90% CIs will be calculated where applicable.

7 DATA CONVENTIONS

(1) Handling of data for PK assessments

If it is necessary to investigate the data handling because of, for example, a protocol deviation (e.g., the blood collection time fell outside the allowable range, the plasma drug concentration could not be measured, or the blood plasma collection procedures were not followed), the study sponsor will decide on the data handling. PK data that are considered "invalid" will be flagged as such in the data listings and will not be included in the summary tables and figures. These data can be excluded from calculation of PK parameters. The PK data handling will be assessed at the data review meeting prior to database lock and a document for PK data handling will be issued.

7.1 Analysis Variable Definitions

7.1.1 Study Subjects

7.1.1.1 Demographic and Other Baseline Characteristics

(1) BMI

BMI will be recalculated using the formula below and reported to 1 DP.

$$\text{BMI (kg/m}^2\text{)} = \text{weight at Day -1 (kg)} / \{\text{height at screening (m)}\}^2$$

7.1.1.2 Medical History

Medical history will be coded according to the MedDRA version 23.1. Definitions of categories are as follows:

(1) Medical history

Any medical conditions which had stopped before the first administration of investigational product.

(2) Complication

Any medical conditions which were present at the first administration of investigational product.

(3) Allergic history

Medical conditions which were reported as allergic history.

7.1.1.3 Concomitant Medication

Medications will be coded according to the WHO (WHO) Drug Global B3 Format September 1, 2020.

Concomitant medication is any medication (including commercially available drugs) other than the investigational product, used between the first administration of investigational product and completion of the end-of-study assessment.

7.1.2 Safety Assessments

7.1.2.1 Adverse Events

Adverse events will be coded according to the MedDRA version 23.1.

(1) Adverse Events (AEs)

An AE is any untoward medical occurrence or unintended sign (including an abnormal laboratory finding), symptoms and disease, occurred after administration and observed in the safety assessment period, regardless of causal relationship with the investigational product. However, if an existing AE worsens in grade or severity, it will be treated as a new AE.

(2) Serious Adverse Events (SAEs)

An AE is treated as a SAE if the seriousness was classified as “serious”.

(3) Adverse Drug Reaction

An AE is considered “adverse drug reaction” if the relationship to the investigational product was assessed to be “reasonable possibility”.

(4) Time to Adverse Events

Time to Adverse Events (days) = AE start date – date of administration in the period of AE occurrence + 1

(5) Duration of Adverse Events

Duration of Adverse Events (days) = AE stop date – AE start date + 1

(6) Period of Adverse Events occurrence

AEs will be assigned to the last administration of the investigational product before the occurrence.

Period I: AEs occurred on or after the time of administration in Period I but before the time of administration in Period II

Period II: AEs occurred on or after the time of administration in Period II but before the completion of end-of-study assessment.

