8.3 Dose and Dosing Regimen

8.3.1 Dose and Dosing Regimen

Details of the administration procedure are specified in a separate procedure.

(1) Oral administration

After having fasted for at least 10 hours, the subjects will drink 100 mL of water 1 hour before receiving the investigational product. After orally administering the investigational product, edaravone oral suspension 105 mg (105 mg/5 mL), have the subject drink 100 mL of water. The subject will be fasted until the completion of blood sampling 4 hours after the administration. Drinking water other than the water provided at the time of administration is prohibited from 1 hour before to 1 hour after investigational product administration. In principle, the subjects should be in a sitting position for at least 2 hours after administration.

(2) Nasogastric administration

Insert a nasogastric tube. It will be confirmed that the nasogastric tube has been passed into the stomach by auscultation and x-ray. After fasting for at least 10 hours, have the subject drink 100 mL of water via a nasogastric tube or orally 1 hour before administering the investigational product. After administering edaravone oral suspension 105 mg (105 mg/5 mL) via a nasogastric tube, flush the tube, and have the subject drink water via a nasogastric tube or orally. The subject will be fasted until the completion of blood sampling 4 hours after the administration. Drinking water other than the water provided at the time of administration is prohibited from 1 hour before to 1 hour after investigational product administration. In principle, the subjects should be in a sitting position for at least 2 hours after administration.

[Rationales for setting]

The dose of edaravone oral suspension was set at 105 mg, which had been confirmed in Study MT-1186-J03 to be bioequivalent in AUC to edaravone intravenous formulation 60 mg in healthy adult subjects.

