8.4 Duration of Dosing

Single-dose: Dosing once each on Period I and II.

[Rationales for setting]

In accordance with the “Guideline for Bioequivalence Studies of Generic Products” (PFSB/ELD Notification No. 0229-10 dated February 29, 2012)[1] and Guidance for Industry: Bioavailability and Bioequivalence Studies Submitted in NDAs or INDs - General Considerations (March 2014)[2], the subjects will receive a single dose.

8.5 Prohibited Matters Before and During the Study Period**8.5.1 Prohibited Matters****(1) Use of medications other than the investigational product**

The use of the investigational product used in this study as well as medications other than a topical anesthetic for nasogastric tube placement and acetylsalicylic acid used as needed is prohibited from 7 days before the start of administration of the investigational product until the completion of end-of-study assessment. However, this does not apply if the investigator (or subinvestigator) determines that it is necessary, such as for the treatment of adverse events.

(2) Smoking and intake of foods and drinks containing specific components

- Smoking or use of any products containing nicotine, alcohol, xanthin, caffeine, or grapefruit: from 24 hours before screening and each visit on Day -1 until hospital discharge.
- Use of any supplements: from 7 days before the start of investigational product administration until the end-of-study assessment.
- Foods or drinks containing poppy seeds: From 72 hours before screening and the hospitalization assessment until completion of prescribed assessment.

[Rationales for setting]

In order to perform pharmacokinetic assessment appropriately, the use of medications other than the investigational product, smoking, drinking alcohol, and intake of some foods are prohibited. This does not apply if the investigator (or subinvestigator) deems it necessary to use medications other than the investigational product, considering safe and ethical performing of this study.

Use of acetylsalicylic acid is permitted because it has been confirmed that there is no reporting that acetylsalicylic acid has inhibiting or inducing effects on sulfate conjugating enzymes and glucuronide conjugating enzymes, which are involved in edaravone elimination.

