8.2.1 Adverse Events

Overall occurrence of AEs will be summarized using the following categories by treatment.

- Subjects with at least one AE
- Subjects with at least one adverse drug reaction
- Subjects with at least one SAE
- Subjects with at least one serious adverse drug reaction
- Subjects with at least one AE leading to discontinuation of study drug
- Subjects with AE leading to death

The following summaries will also be presented by treatment.

- AEs by SOC and PT
- Adverse drug reactions by SOC and PT
- AEs by SOC, PT and severity

These will be subject-based summaries - multiple occurrences of the event with the same SOC and/or PT within a subject will be counted once in the summaries by SOC and PT; multiple occurrences of the event with the same SOC and/or PT but different severity within a subject will be counted once in the maximum severity category (severe > moderate > mild).

To summarize by treatment, the AE occurred under PO/NGT treatment period will be counted as PO/NGT treatment. Period of AE occurrence is defined in 7.1.2.1 (6).

The followings will be listed.

- AE
- SAE

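### Tube-insertion adverse events that start before the NGT dose are counted as oral or not counted at all, so the by-route tables understate any NGT excess

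*SAP*

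**What the plan says.** Protocol 8.3.1(2) begins NGT administration with insertion of the tube, followed by a position check: "It will be confirmed that the nasogastric tube has been passed into the stomach by auscultation and x-ray". The water given one hour before the dose may go through the tube, so the tube may already be in place by then. The section gives no day or hour for insertion and leaves procedural detail to a separate document. Protocol 8.5.1 permits "a topical anesthetic for nasogastric tube placement".

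SAP 7.1.2.1(6) sets the attribution rule: "AEs will be assigned to the last administration of the investigational product before the occurrence". It then defines the first window: "Period I: AEs occurred on or after the time of administration in Period I but before the time of administration in Period II". SAP 8.2.1 carries this into the tables: "To summarize by treatment, the AE occurred under PO/NGT treatment period will be counted as PO/NGT treatment". Time to onset, in 7.1.2.1(4), is counted from the "date of administration in the period of AE occurrence".

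On collection, SAP 3.3 footnote b has serious events collected from consent, but for the rest: "Collecting the other adverse events was started after the first administration of the investigational product". Protocol 9.1 (footnote b), 9.2.5 and 9.2.5.2 set the same starting point, and SAP 7.1.2.1(1) limits an AE to onset after administration. SAP 7.1.1.2 defines a complication as "Any medical conditions which were present at the first administration of investigational product". SAP section 10 lists departures from the protocol and makes no exception for tube-related events.

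**The concern.** Drug and dose are the same in both treatments; only the route differs, and inserting the tube is part of the NGT route. A last-dose rule suits drug effects, but here it misplaces events caused by the procedure that comes before the dose.

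- **PO-NGT group.** An insertion event before the Period II dose falls in the Period I window and is tabulated as oral. If insertion is on Day 4, its time to onset is 4 - 1 + 1 = 4 days, counted from the oral dose.
- **NGT-PO group.** The same event precedes the first dose. If non-serious, it is outside the AE definition, the safety assessment period and the collection window. At most it appears as an examination finding or a complication. If serious, it is collected, but neither period window covers it.

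Both errors lower the NGT-minus-oral difference, so they add rather than cancel. Safety and tolerability form the secondary objective, and AE incidence by route is the planned summary for it.

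**Working it through.** **Inputs from the documents.** There are 36 subjects, 18 per sequence (SAP 3.2.1). The stated sample size reproduces: 30 completers + 6 dropouts = 36 = 18 + 18. The documents give no expected AE rate for this trial.

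**Assumptions.** Let p be the risk of an insertion AE starting before the NGT dose, r the extra NGT risk with onset after dosing, and q the background risk per period. No values for p or r are given, so a range is shown. For q, the earlier oral-versus-intravenous crossover (protocol section 1) reports 2 AEs in 42 subjects over two periods: q = 2/(42 × 2) = 2/84 = 2.4%. This takes the two events as two separate subject-periods. The components are treated as independent, and all 36 subjects are taken as dosed in both periods.

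**As the SAP tabulates:**
- NGT = 1 - (1-q)(1-r)
- PO = average of 1 - (1-q)(1-p) in PO-NGT and q in NGT-PO
- Difference, NGT minus PO = (1-q)(r - p/2)

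**With insertion events credited to NGT:**
- NGT = 1 - (1-q)(1-p)(1-r); PO = q
- Difference = (1-q)(r + p - rp)

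Tabulated minus true is -(1-q)p(1.5 - r), which is negative for any p above zero. The tabulated difference is zero at r = p/2 and reversed only if r < p/2.

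**Example, p = 10%, r = 0.** Tabulated PO is 7.3% (2.6/36) and NGT 2.4% (0.9/36), a difference of -4.9 points. True NGT is 12.1% (4.4/36) and PO 2.4%, a difference of +9.8 points.

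| p | r | Tabulated NGT - PO (points) | True NGT - PO (points) |
|---|---|---|---|
| 5% | 0 | -2.4 | +4.9 |
| 5% | 5% | +2.4 | +9.5 |
| 10% | 0 | -4.9 | +9.8 |
| 10% | 5% | 0.0 | +14.2 |
| 10% | 10% | +4.9 | +18.5 |
| 20% | 0 | -9.8 | +19.5 |
| 20% | 10% | 0.0 | +27.3 |
| 20% | 20% | +9.8 | +35.1 |

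The expected number of subjects with an insertion event credited to oral is 18p: 0.9, 1.8 and 3.6 for p = 5%, 10% and 20%. If the events are non-serious, the same expected number is missing from the NGT-PO group.

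**Chance that the table shows more oral than NGT subjects with an AE** (36 subjects, 200,000 simulated trials):
- p = 10%: 76% at r = 0, 41% at r = 5%, 18% at r = 10%
- p = 20%: 93% at r = 0, 43% at r = 10%, 10% at r = 20%

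**In whole subjects.** With one such event in each sequence and no other AE, the table reads NGT 0, PO 1 (-1/36 = -2.8 points) instead of NGT 2, PO 0 (+2/36 = +5.6 points).

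**If only the PO-NGT group can be corrected**, the difference becomes (1-q)(r + (p/2)(1-r)): +4.9 points at p = 10%, r = 0, and +14.2 at p = r = 10%. That is still too small, but never reversed.

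**The case against.** The strongest reply is that the size is unknown. Without a value for p there may be no bias at all, and at p = 5% fewer than one subject is expected to move to oral. This stands: the direction follows from the text, but the size does not. Reversal is also demanding. It needs r < p/2, so more than two-thirds of the tube-event risk must fall before the dose. Every reversed row above has r = 0, which is an extreme case because the tube stays in place for dosing and flushing.

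It can also be argued that the secondary objective concerns a single dose of the suspension, not tube placement, so that a post-dose AE definition with last-dose attribution is coherent, and that no AE difference is formally estimated. That would justify leaving insertion events out. It does not justify counting those in one sequence as oral while dropping those in the other.

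Other points stand in part. PO-NGT events can be traced, because AEs and physical examinations are listed and in-hospital onset times are recorded; non-serious NGT-PO events cannot be recovered from an AE listing. The separate administration procedure may fix the insertion time, but unless no event can start before the dose, the attribution rule still misplaces it. An insertion event that worsens after the dose becomes a new AE and then counts under NGT, but its first onset is still misplaced. The SAP describes collection in the past tense, so protocol and CRF changes may come too late.

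**Conclusion.** The concern holds. No AE that starts between tube insertion and the NGT dose can be tabulated under NGT at that onset; in the PO-NGT group it is credited to the comparator route. For any p above zero the all-cause NGT excess is understated, and it changes sign in expectation if r < p/2. Over p from 5% to 20% and the values of r shown, the expected shortfall runs from about 7 points (p = r = 5%: +2.4 against +9.5) to about 29 points (p = 20%, r = 0: -9.8 against +19.5). These sizes rest on assumed p and r, independent components and full dosing in both periods. The mechanism does not rest on those assumptions.

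The scope is limited. The tables are descriptive, PK results are unaffected, and the adverse drug reaction tables are largely unaffected because they require a reasonable possibility of drug cause. This should be fixed, but it does not threaten the primary objective.

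**What to change.** - **SAP 7.1.2.1(6).** Add that an AE with onset from the start of tube insertion up to the NGT dose counts under NGT when judged related to the tube procedure, including the topical anesthetic. List these separately as pre-dose procedure events. All other AEs stay with the last dose, so late events of the oral dose are not moved. The wording should cover serious events as well, since a serious pre-dose event in the NGT-PO group otherwise has no period.
- **Protocol 9.2.5.2 and footnote b in 9.1.** Collect non-serious AEs from tube insertion in subjects who receive NGT in Period I, and record the insertion time in the CRF.
- **If collection is already complete.** Apply the SAP rule to the PO-NGT group before database lock, using the recorded onset times. State in the SAP and the report that non-serious pre-dose insertion events were not collected in the NGT-PO group, so the NGT rate is understated.

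The cost is SAP wording, one CRF time field, one procedure-relatedness judgment per affected AE (made open-label) and, if collection is still open, a protocol clarification. NGT all-cause rates will look less favourable. Earlier collection in NGT-first subjects makes Period I collection unequal between sequences; the separate listing keeps that visible. The NGT-PO half cannot be recovered once collection has closed.

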7.1.2.2 Laboratory Tests

(1) Clinically relevant values flag

Clinically relevant values flag will be attached to the values out of normal range. (L=Lower than normal range, H=Higher than normal range or A=Abnormal).

(2) Laboratory test values below the limit of quantification

Any BLQ data will be treated as LLOQ/2 in summary statistics.

7.1.2.3 12-Lead ECG

(1) Criteria for pre-defined limit

12-lead ECG:

- QTcF > 500 msec
- 500 >= QTcF > 480msec
- 480 >= QTcF > 450msec
- QTcF <= 450 msec
- Change from baseline in QTcF > 60 msec
- Change from baseline in QTcF > 30 msec

7.1.3 Pharmacokinetics Evaluation

7.1.3.1 Plasma Concentration

For the calculation of the summary statistics, concentration values reported as BLQ will be set to 0. In figures, concentration values reported as BLQ will be plotted as 0 in linear scale and not plotted in semi-logarithmic scale.

7.1.3.2 Pharmacokinetic Parameters

For the calculation of PK parameters, actual sampling time (in hours rounded to 3 decimal places) relative to dosing should be used. If the sampling was performed before dosing, time after dosing will be set to 0. When k_{el} is missing (or cannot be determined), $t_{1/2}$, $AUC_{0-\infty}$, $AUC\%_{ex}$, CL/F , MRT , V_z/F and V_{ss}/F will not be calculated.

(1) Below the limit of quantification

Concentration below the limit of quantification (BLQ) will be set to 0.

(2) Calculation of AUC

Timepoints with missing concentration data will be ignored. Concentration value at the end time of partial AUC will be calculated by linear-linear trapezoidal rule or by extrapolation using elimination rate constant, if there is no valid data exactly at the time.

(3) Calculation of V_{ss}/F

Pharmacokinetic parameter of V_{ss}/F will be calculated as follows:

$$V_{ss}/F = MRT \times CL/F$$

7.2 Analysis Visit Definitions

(1) Non-PK related

Analysis visit window is not defined. By-visit summaries will be based on nominal visit or timepoint.

Study day is the relative day to the first treatment. Day -1 is the day before the first treatment, Day 1 is the day of the first treatment, and Day 2 is the next day.

Except for laboratory tests, Day 1 pre dose will be the baseline for Period I and Day 4 pre dose will be the baseline for Period II. For laboratory tests, Day -1 will be the baseline.

(2) PK related

Analysis time point and allowable range is defined below.

Analysis Time Point	Window
Predose	Within 60 min before dosing
0.083 h	Nominal time \pm 1 min
0.25, 0.5, 0.75, 1, 1.5, 2, 4, 6, 8, 10, 12 h	Nominal time \pm 5 min
24, 36, 48 h	Nominal time \pm 15 min

